# 8.1.1.1.2 14-Day EBA Estimate Through Linear Mixed Effects Modeling

Another way to estimate the 14-Day EBA is through a linear mixed effect model, using log10CFU/mL as outcome variable, treatment group,

intercept and slope for day includes a random component for each subject.

The model can be specified in formula as follows:

Statistical Analysis Plan

The model can be fit using SAS PROC MIXED procedure.

The estimated EBA is obtained by taking the negative sign of the slopes for each treatment group. Either the Fieller's method or Taylor's method described in Sections 8.1.1.2 will be used in estimating 95% CI for the EBA ratios between treatment groups. The parameters needed as input for the two algorithms include negative slope and the variance covariance matrix for the slopes, represented using symbols  $\hat{\theta}_1$ ,  $\hat{\theta}_2$   $\hat{\sigma}_{11}$ ,  $\hat{\sigma}_{22}$ .

Similar analyses will be performed for log10LAM pg/mL and TTD endpoints (in greater detail in Section 8.2) except that, in estimating the EBA for TTD, a negative sign is not applied to the slope for TTD. For Stage 2, the same model is used, with the groups for Stage 2 being Stage 1 + Stage 2 RHEZ, OPC + DLM, OPC + BDQ, OPC + DLM + BDQ.

# 8.1.1.2 Confidence Interval Estimation for EBA Ratio Between OPC and RHEZ

The treatment mean and standard error (the square of which is the estimated  $\hat{\sigma}_{11}$ ,  $\hat{\sigma}_{22}$ ) calculated using methods in Section 8.1.1.1 will be used to estimate EBA ratio using Fieller's or Taylor's methods described in this section.

#### 8.1.1.2.1 Estimate EBA Ratio with Fieller's method

Let  $r = \theta_1/\theta_2$  and  $\theta_1$  and  $\theta_2$  stands for the 14-Day EBA for two treatment groups. It is assumed that the estimators  $(\hat{\theta}_1, \hat{\theta}_2)$  follow a bivariate normal distribution with mean  $(\theta_1, \theta_2)$  and estimated variance covariance  $\hat{\sigma}_{11} = var(\hat{\theta}_1), \hat{\sigma}_{22} = var(\hat{\theta}_2)$ , and  $\hat{\sigma}_{12} = cov(\hat{\theta}_1, \hat{\theta}_2)$ . For two-point estimate from Section 8.1.1.1.1, the parameter estimates  $\hat{\theta}_1$ ,  $\hat{\theta}_2$ ,  $\hat{\sigma}_{11}$ ,  $\hat{\sigma}_{22}$  comes from summary statistics (mean and square of the standard errors), and covariance between EBA for two treatment groups  $\hat{\sigma}_{12}$ 

method SAS macro is provided in Appendix 5 for reference.

### 8.1.1.2.2 Estimate EBA Ratio with Taylor's (Delta) method

Formula (2) can be used to estimate the  $100(1-\alpha/2)$  CI for the EBA ratio (IMP-1 divided by IMP-2). For two-point estimate from Section 8.1.1.1.1, the parameter estimates  $\hat{\theta}_1$ ,  $\hat{\theta}_2$ ,  $\hat{\sigma}_{11}$ ,  $\hat{\sigma}_{22}$  come from summary statistics (mean and square of the standard errors), and covariance between EBA for two treatment groups  $\hat{\sigma}_{12}$ The  $\hat{\theta}_1$ ,  $\hat{\theta}_2$ ,  $\hat{\sigma}_{11}$ ,  $\hat{\sigma}_{22}$ ,  $\hat{\sigma}_{12}$  can be estimated using the same method from Section 8.1.1.2.1.

[figure not shown]
$$\frac{\hat{\theta}_1}{\hat{\theta}_2} \pm t_q \frac{\hat{\theta}_1}{\hat{\theta}_2} \sqrt{\frac{\hat{\sigma}_{11}}{\hat{\theta}_1}^2 + \frac{\hat{\sigma}_{22}}{\hat{\theta}_2}^2 - \frac{2\hat{\sigma}_{12}}{\hat{\theta}_1\hat{\theta}_2}} \tag{2}$$

# 8.2 Secondary Efficacy Endpoint Analyses

The analyses of the secondary endpoints of the slope of change in log10LAM pg/mL values and change in Time to detection (TTD) in stage 1 will be conducted in a way similar to comparisons of change in log10CFU/mL specified in Section 8.1.1.1 for Stage 1.

[figure not shown]
Stage 2 EBA analyses will be based on  $log_{10}CFU/mL$ ,  $log_{10}LAM pg/mL$  (raw and processed) and TTD.

Treatment group comparisons in Stage 2 are:

Statistical Analysis Plan

22 of 58

The same analysis methods as described in Section 8.1.1 will be used for the comparisons of (1) and (2) above mentioned. Only the data of these three treatment groups in all efficacy analysis set in Stage 2 will be included in this analysis (that is, Stage 2 RHEZ arm, and Stage 1 arms are not included in the analysis).

### LAM and TTD analyses:

The change from baseline in LAM and TTD will be analyzed using the same methods specified for CFU.

#### LAM:

More details of analysis data derivation for LAM is provided as follows.

Two LAM assessments are available at each visit, one on raw sputum (LAM(raw)), and one on processed decontaminated sputum (LAM(processed)). Baseline LAM is calculated as the average of Day -2 and Day -1 and the log10 of the average is used in EBA derivation. If one sample has a missing value then the nonmissing sample is used. The lower limit of quantification (LLoQ) of LAM test is 15 pg/mL. If a sample result has a reported value below the LLoQ (< 15 pg/mL) and does not indicate "NO RESULT", the value 15 pg/mL is used in the analyses for that visit.

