Following review of the safety, tolerability, PK, and efficacy data from Cohort 1, a decision will be made to start Cohort 2. Cohort 2 will be completed as described above for Cohort 1 at the selected dose of OPC-167832. The same process will be followed for Cohort 3 after the completion of Cohort 2 and for Cohort 4 after the completion of Cohort 3.

The safety, tolerability, PK, and efficacy ( ) data from each cohort will be reviewed by the trial review team at the end of each cohort. Once all the data for dose selection for the next cohort are available, the data collected from each cohort will be provided to the trial review team. The data will be evaluated to determine if (i) the dose level for the next cohort will be escalated, (ii) the dose level from the previous cohort will be repeated, or (iii) the dose level will be decreased. The dose of OPC-167832 will not exceed the highest tolerated dose studied in the SAD trial, ie, 480 mg.

The trial review team will consist of Otsuka Pharmaceutical Development & Commercialization, Inc. (OPDC) staff, including the project leader, Clinical Management representative(s), Global Pharmacovigilance representative(s), Clinical Pharmacology representative(s), OPDC medical monitor; the principal investigator (or designee); Microbiology and Diagnostic Director; and other staff, as needed.

[figure not shown]
Decisions to proceed to the next dose level should be based on, but not limited to, the following safety aspects:

- No death assessed as related to OPC-167832
- No more than 2 subjects with Grade 4/5 AEs (“Division of AIDS [DAIDS] Table for Grading the Severity of Adult and Pediatric AEs” [[Appendix 3](#)]) assessed as related to OPC-167832

For efficacy, the selection of the dose level for each cohort after Cohort 1 will be assisted by the results of the Otsuka TB LAM ELISA instead of solid media culture, since those results are available in near real time and will facilitate faster decisions.

The trial design schematic is presented in [Figure 3.1.1-1](#).

Protocol 323-201-00003

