#### **3.5.2.4 Pharmacokinetics/Pharmacodynamics - Stage 1 and Stage 2**

The maximum effect and  $EC_{80}$  for OPC-167832, regardless of dose level, will be determined from an exposure-response analysis of the results from the Otsuka TB ELISA LAM.

The relationship between QT interval and plasma concentrations of OPC-167832 (stage 1) and OPC-167832 when administered with delamanid and/or BDQ (stage 2) will be evaluated.

Protocol 323-201-00003

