The study day of baseline is set to be 0 no matter whether the baseline comes from Day - 2 or Day -1 or the average. The derived analysis CFU is log10 transformed in the calculations of decline in bacteria load. The early bactericidal activity (*EBA*) is determined by the rate of decline in log10CFU/mL during the first 14 days of treatment. The rate of decline will be estimated using both a two-point calculation (day 14 and day 0 (baseline)) as well as a linear-regression based approach as discussed in Section 8.1.1.1.1 and Section 8.1.1.1.2.

and

Version Date: 16 May 2022

Protocol 323-201-00003

The effect size for EBA for IMP-1 group relative to that of IMP-2 group is expressed as the ratio of EBA as shown in formula (1). Either Fieller's method or Delta method as described in Sections 8.1.1.2  will be used in the estimation of the confidence interval of the ratio

$$\frac{EBA_{0-14,IMP1}}{EBA_{0-14,IMP2}}\tag{1}$$

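### SAP 8.2 sets LAM results below the 15 pg/mL quantification limit to 15, which understates decline and, with comparable baselines, pulls LAM EBA ratios toward 1 to the extent that results fall below 15

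*SAP*

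**What the plan says.** SAP 8.2 (LAM) states: "The lower limit of quantification (LLoQ) of LAM test is 15 pg/mL". For a reported value under that limit, other than one marked as having no result, "the value 15 pg/mL is used in the analyses for that visit". On the baseline it says "Baseline LAM is calculated as the average of Day -2 and Day -1", with log10 taken after averaging. The substitution rule is not confined to post-baseline visits.

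The analysis follows CFU: "The change from baseline in LAM and TTD will be analyzed using the same methods specified for CFU". Those methods (SAP 8.1.1.1) are a two-point 14-day EBA and a linear mixed model in which each subject has a random intercept and slope for day. SAP 8.1.1 then forms the comparison: "The effect size for EBA for IMP-1 group relative to that of IMP-2 group is expressed as the ratio of EBA", with a Fieller or delta-method interval.

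LAM EBA is a secondary endpoint in both stages (Protocol 3.5.2.1). SAP 8.2 applies the Stage 2 EBA analyses to raw and processed LAM. The Stage 2 comparisons in Protocol 7.4.2 include the triple combination against each double combination.

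**The concern.** A result below 15 pg/mL is left-censored: all that is known is that it is under 15. The SAP gives it the largest value it could have and analyses it as a measurement. For a post-baseline visit this can only make the subject's decline look smaller, and the interval does not reflect that the value is unknown. The SAP is not uniform here either. SAP 9.3 sets safety laboratory values reported as below a cutoff to half the cutoff, while LAM is set to the cutoff itself, and no reason is visible.

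The comparison most exposed is triple against double combinations in Stage 2. If the third drug speeds clearance, more of the triple arm's samples reach the floor and its added effect on LAM is understated. Those arms are randomised concurrently, so their baselines are comparable in expectation.

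**Working it through.** **The plan's own figure.** Protocol 7.4.1.1.1 gives 14-day declines of 0.84 log10 CFU (delamanid 200 mg) and 1.44 (RHEZ). 0.84/1.44 = 0.583, which reproduces its 58%. No figure is given for LAM.

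**Inputs from the documents.** Limit 15 pg/mL, so c = log10(15) = 1.176. Sampling at baseline (Day 0) and Days 2, 4, ..., 14.

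**Assumptions, not in the documents.** LAM falls linearly on the log10 scale by the CFU amounts: 1.44/14 = 0.1029 per day (RHEZ) and 0.84/14 = 0.0600 (slower arm). Protocol Section 1 says LAM and CFU declines correlate closely but gives no number. Baseline SD is 0.7 log10, slope SD 0.03 per day, residual SD 0.25, all normal. Median baseline varies from 316 to 10,000 pg/mL. A least-squares slope stands in for the mixed model, whose formula is not visible.

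**Where the floor starts to bite.** The arm median reaches 15 at Day 14 if the median baseline is 15 × 10^0.84 = 104 pg/mL (slower arm) or 15 × 10^1.44 = 413 (RHEZ).

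**Expected floored value on day d.** Let m be the true mean on day d, s = √(0.7² + (0.03d)² + 0.25²) and z = (m − c)/s. Then

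E = c + (m − c)Φ(z) + sφ(z), and the share below the limit is 1 − Φ(z).

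RHEZ, median baseline 1,000, Day 14: m = 3 − 1.44 = 1.56; s = √(0.49 + 0.1764 + 0.0625) = 0.854; z = 0.384/0.854 = 0.450. The share below 15 is 33%. E = 1.176 + 0.384 × 0.674 + 0.854 × 0.361 = 1.743, so the Day 14 mean is 0.18 log10 too high. For the slower arm it is 0.05 too high.

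The slope is −Σ(d − 7)E/168, over the eight days, with Day 0 floored too:

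| Median baseline (pg/mL) | Day 14 below 15: RHEZ / slower arm | RHEZ slope (true 0.1029) | Slower slope (true 0.0600) | Ratio (true 0.583) |
|---|---|---|---|---|
| 10,000 | 5% / 1% | 0.1018 | 0.0598 | 0.59 |
| 3,162 | 15% / 4% | 0.0987 | 0.0591 | 0.60 |
| 1,000 | 33% / 12% | 0.0909 | 0.0566 | 0.62 |
| 316 | 55% / 29% | 0.0757 | 0.0502 | 0.66 |

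A simulation of 200,000 subjects per scenario gave ratios of 0.588, 0.597, 0.621 and 0.662.

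**An arm faster than RHEZ.** With a hypothetical 2.0 log10 decline against 1.44 (simulated two-point EBA, residual SD 0.3), the ratio goes from 1.38 to 1.34 at 10,000, 1.37 to 1.23 at 1,000 and 1.38 to 1.17 at 300. With equal declines and baselines it stays at 1.

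**Unequal baselines.** Keep RHEZ at 1,000 and start the slower arm 0.6 log10 lower. Both arms then have 33% below 15 at Day 14, but the slower arm loses more in proportion: 0.0484/0.0909 = 0.53, away from 1. The chance standard error of the baseline difference at 14 v 16 subjects is 0.7 × √(1/14 + 1/16) = 0.26 log10. In simulated trials of that size (two-point EBA, 0.84 v 1.44, medians 300 to 3,000) the ratio moved away from 1 in 19% to 21% of runs.

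**Precision.** The variance of one subject's slope is 0.03² + 0.25²/168 = 0.00127. Standard errors are 0.0095 (n = 14) and 0.0089 (n = 16). The delta-method 95% half-width is 1.96 × 0.583 × √((0.0095/0.0600)² + (0.0089/0.1029)²) = 0.21.

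**Does a censored model help?** In 25 simulated 16-subject RHEZ arms at a 1,000 pg/mL baseline (true slope 0.1029), substitution gave a mean slope of 0.0931 (SD 0.0096) and censored maximum likelihood 0.1044 (SD 0.0108). Combined error: √(0.0098² + 0.0096²) = 0.0137 against √(0.0015² + 0.0108²) = 0.0109.

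**The case against.** The rule is prespecified and transparent, and it resembles the SAP's 5 CFU/mL and 42-day TTD limits. Entry requires a smear of at least 1+, which favours high bacterial loads, and at high baseline LAM the effect is negligible. Even at 316 pg/mL the shift in the ratio (0.08) is well inside the half-width of 0.21, and the trial is not powered for formal comparisons. A censored model leans on normality below the limit in arms of 14 to 16. All of that stands. It argues for adding a censored analysis rather than replacing the planned one. It does not remove the bias, which more precision would not cure, and the documents give no LAM distribution to show that results below 15 will be rare.

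Three stronger readings are tempting, and the documents do not support them.

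- **The ratio is always pulled toward 1.** It is not when the slower arm starts lower. Randomisation is unstratified, Stage 1 cohorts are sequential and RHEZ is pooled, so equal baselines are not assured. A floored baseline would also overstate decline.
- **Stage 1 dose selection was distorted.** Protocol 3.1.1 says that selection "will be assisted by the results of the Otsuka TB LAM ELISA instead of solid media culture", but alongside safety, tolerability and PK. Neither that section nor Protocol 7.8.1 states a rule for results below the limit. Any move from the stated Stage 2 dose rests on plasma concentrations and log10 CFU.
- **The LAM Emax and EC80 are biased.** Protocol 3.5.2.4 says these "will be determined from an exposure-response analysis of the results from the Otsuka TB ELISA LAM", but SAP 6.2.3 and 11 place that model in a separate plan and report. Its handling of low values is unknown.

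The text of SAP 8.3, Appendix 6 and Appendix 7, and parts of 8.1.1.1.2 and 8.2, cannot be seen. A censored analysis or a count of low results could be there.

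**Conclusion.** The point holds in conditional form. Substituting 15 understates the LAM decline of any subject whose post-baseline result is replaced. With comparable baselines, and to the extent that results fall below 15, the faster-clearing arm is understated more and the LAM EBA ratio moves toward 1. Under the stated assumptions the shift is under 0.01 at a median baseline of 10,000 pg/mL, about 0.04 at 1,000 and about 0.08 at 316, for a true ratio of 0.583. Every one of these sizes depends on LAM levels and SDs that the documents do not give. The reach is the secondary LAM EBA endpoints, including triple against double combinations in Stage 2. The primary CFU endpoint is untouched by this rule.

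**What to change.** In SAP 8.2 (LAM), keep the substitution analysis and prespecify beside it the same random intercept and slope model with results below 15 pg/mL treated as left-censored at 15, for example in SAS PROC NLMIXED. Report LAM EBA and the EBA ratios from both. Tabulate the number of results below 15 by arm, visit and matrix (raw and processed), so that a reader can see whether the two analyses could differ. If these items are already in the parts of the SAP that are not visible, no change is needed.

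The cost is SAP wording and some programming, a slightly larger slope standard error (0.0108 against 0.0096 per day in the small-arm check above), and reliance on a normal distribution below the limit. Trial conduct does not change.

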#### TTD:

TTD is the time from start of inoculation of a sputum sample until a MGIT machine detects a positive signal during the 42-day incubation period. One TTD measurement, reported in days and hours, is taken at each of the visits at Days -2, -1, 2, 4, 6, 8, 10, 12 and 14.

The TTD values in Days will be calculated as "days + hours/24" to be used in deriving the analysis values of TTD. Pure MTB positive MGIT culture is MTB confirmed with no growth of contaminants.

[figure not shown]
Baseline TTD will be derived using the Day -2 and Day -1 MGIT culture with a pure positive result for *Mycobacterium tuberculosis*. If both days are pure positive, the average of Day -2 and Day -1 will be used as baseline TTD. If only one day is pure positive, the

TTD from that day is used as baseline. If neither day is pure positive, the baseline TTD is set to missing.

The postbaseline TTD analysis values from Day 1 and later will be derived based on the MGIT culture result as follows:

- 1. When a MGIT culture result is negative for MTB complex, TTD is set to 42 days (the value for time-to-result with negative culture).
- 2. If the MGIT culture is pure positive for MTB, but for some reason the TTD took longer than 42 days, TTD will be capped at 42 days.
- 3. TTD values from MGIT cultures with the following qualitative results will be set to missing:
  - Contaminated
  - Positive for MTB complex and contaminated
  - No TB growth but positive for other mycobacteria
  - Unknown.

All analyses will be presented by treatment groups for Stage 1, and Stage 2 with a combined RHEZ group from Stage 1 and Stage 2.

# 9 Safety Analyses

Safety data will be summarized by randomized treatment using descriptive statistics (number, median, mean, SD, minimum, and maximum) for numeric variables and frequency and count for discrete variables.

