### **3.13 Protocol Deviations**

In the event of a major deviation from the protocol due to an emergency, accident, or mistake (eg, IMP or RHEZ dispensing or subject dosing error or concomitant medication), the investigator or designee will contact the sponsor at the earliest possible time by telephone. The investigator, medical monitor, and sponsor will come to a joint decision as quickly as possible regarding the subject’s continuation in the trial. If the decision reached is to allow the subject to continue in the trial, this must be documented by the investigator and the sponsor, and approved or disapproved by the medical monitor.

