### 7.2 Datasets for Analysis

The PK population will include all subjects with adequate data for deriving the PK parameters.

Safety analysis will be conducted based upon the safety population. All subjects who received any dose of IMP or RHEZ will be included in the safety population.

Protocol 323-201-00003

Efficacy analyses will be conducted based upon the modified intent-to-treat (MITT) population. The MITT population will include all subjects who were quantitative culture-positive at baseline and met all of the inclusion criteria.

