### **7.6 Safety Analysis**

Safety data will be summarized by randomized treatment using descriptive statistics (number, median, mean, SD, minimum, and maximum) for numeric variables and frequency and count for discrete variables. Incidence of clinically notable values will be summarized where applicable. Safety assessments will also be listed by subject.

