### 5.2 Safety Analysis Set

Safety Analysis Set includes subjects who are randomized and take any dose of IMP (OPC-167832 or Delamanid or Bedaquiline or RHEZ).

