#### 9.2 Adverse Events

All AEs will be coded by Medical Dictionary for Regulatory Activities (MedDRA; Version 22 or newest available) system organ class and preferred term. Treatment-emergent AEs (TEAE) are defined as AEs that occurs after the initiation of trial treatment; or an event or pre-existing medical problem that has changed adversely in nature or severity from baseline in a subject while receiving trial treatment. The frequency and percentage of subjects with the following events will be summarized by SOC, MedDRA preferred term, severity and treatment:

- Treatment-emergent AEs (TEAEs)
- TEAEs potentially causally related to the IMP or RHEZ
- TEAEs with an outcome of death
- Serious TEAEs
- TEAEs leading to discontinuations of the IMP
- TEAEs by DAIDS grading
- non-serious TEAEs (NSAE)

All AEs will be presented in a listing. The listing of death due to AE, serious AE and TEAE leading to discontinuation will also be provided. In addition, the number and frequency of TEAE incidences will be summarized for serious TEAE, serious study medication related TEAE and non-serious TEAE. The analyses on AEs will be performed separately for Stage 1, and Stage 2 with a combined RHEZ group from Stage 1 and Stage 2.

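### Safety tables are grouped by randomised treatment, so a subject who took another arm's regimen would be tabulated in the wrong arm; grouping by treatment received is a cheap improvement

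*SAP*

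**What the plan says.** SAP section 9 opens with one grouping rule for safety output: "Safety data will be summarized by randomized treatment using descriptive statistics". Protocol 7.6 carries the same rule ("Safety data will be summarized by randomized treatment using descriptive statistics (number, median, mean, SD, minimum, and maximum"), and the safety paragraph under Statistical Methods in the synopsis repeats it.

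Membership of the safety set is defined separately. SAP 5.2 reads "Safety Analysis Set includes subjects who are randomized and take any dose of IMP (OPC-167832 or Delamanid or Bedaquiline or RHEZ", and protocol 7.2 reads "All subjects who received any dose of IMP or RHEZ will be included in the safety population". Both settle who is counted; neither says in which column.

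The detailed sections do not override the rule. In SAP 9.2 the adverse event frequencies "will be summarized by SOC, MedDRA preferred term, severity and treatment". The laboratory, vital-sign and ECG sections (9.3, 9.4, 9.6) speak only of treatment groups, with RHEZ from the two stages combined. None of them defines treatment as treatment received.

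Protocol 3.13 names "IMP or RHEZ dispensing or subject dosing error" among its examples of a major deviation and allows for a joint decision that the subject continues. Protocol 10.3 also lists major dosing errors as a deviation category.

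**The concern.** For efficacy, analysing by randomised arm protects the comparison. For safety the question is what happened to people who took a given regimen, and the randomised label answers it only when it matches what was swallowed.

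The mismatch matters here for three reasons. Safety and tolerability is a primary endpoint in both stages (protocol 3.5.1.6) and the first-listed primary objective of Stage 2 (protocol 2.3.1.2). The three Stage 2 investigational arms all contain OPC-167832 and differ only in whether delamanid, BDQ or both are added, so one added or left-out component, if sustained, turns one arm's regimen into another's. And which component was taken bears on the result: protocol 1.3.2 attributes QT prolongation to delamanid, and SAP 9.6 and Appendix 4 tabulate QTc outliers by treatment group.

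**Working it through.** The plan gives no figure to reproduce on this point. The check has three parts: the rule, the weight of one misplaced subject, and whether another planned output would correct the tables.

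**Inputs** (SAP section 4; protocol 3.1.1 and 3.1.2). Stage 1 has 4 cohorts of 18, each 14 OPC-167832 and 4 RHEZ: 4 × 18 = 72. Stage 2 is 14:14:14:4: 3 × 14 + 4 = 46. Total 72 + 46 = 118. Pooled RHEZ: 4 × 4 + 4 = 20.

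**Weight of one subject** = 1/n. For an investigational arm, 1/14 = 7.1%. For the pooled RHEZ group, 1/20 = 5.0%.

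**Effect on the tables.** Assume one subject takes another arm's regimen throughout and has the only event of its type.

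| Case | By randomised treatment | By treatment received |
|---|---|---|
| Assigned to one Stage 2 investigational arm, took another | assigned arm 1/14 = 7.1%; arm taken 0/14 | assigned arm 0/13; arm taken 1/15 = 6.7% |
| Assigned to RHEZ (pooled), took an investigational regimen | RHEZ 1/20 = 5.0%; arm taken 0/14 | RHEZ 0/19; arm taken 1/15 = 6.7% |
| Assigned to an investigational arm, took RHEZ | assigned arm 1/14 = 7.1%; RHEZ 0/20 | assigned arm 0/13; RHEZ 1/21 = 4.8% |

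In each case the event changes column.

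**Other outputs.** The exposure table (SAP 9.1) uses the Randomized Analysis Set and counts exposure to any of OPC-167832, delamanid or BDQ from first to last date, so it would not show a wrong or absent component. SAP 7.4 plans no compliance analysis. SAP 7.6 summarises deviations by type and lists them, and SAP 9.1 and 9.2 list dosing and adverse events by subject. These make the error traceable but do not move the event.

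**Which classification rule works.** A majority counted over all of Days 1-14 needs at least 8 days on one regimen, so a subject who stops on Day 5 cannot be classified. Counted over the days actually dosed, that subject needs 3 of 5. A subject given an unassigned drug on 6 of 14 days remains in the assigned arm under either count, because 6 is less than 8. A flag and listing are therefore needed alongside the classification.

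**The case against.** The strongest reply is that the event is improbable and would not be concealed. All dosing is inpatient with a hand and mouth check, and time and dose are recorded (protocol 3.12). Randomisation is central, the trial is open-label, and sponsor-supplied bottles disclose the compound (protocol 8.1). Stage 1 cohorts run in sequence, so the only concurrent confusion there is OPC-167832 with RHEZ. RHEZ is a weight-banded combination tablet with its own meal timing, hard to mistake for the investigational drugs. Analyses are descriptive and unpowered.

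Most of this stands, and it limits the point. The hand and mouth check confirms swallowing rather than correct dispensing, so a wrong component remains possible. Low probability makes the point minor; it does not make the randomised label the better grouping for safety.

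A reader might go further in four ways that the documents do not support:

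- That a wrong component is the likely error. No error rate is given anywhere, so it is plausible only.
- That one subject could shift RHEZ by 1/4 = 25 points. That needs the four Stage 2 RHEZ subjects shown alone, whereas SAP 9.2, 9.3, 9.4 and 9.6 combine RHEZ across stages. Section 9.5, on physical examinations, is worded slightly differently but also calls for a combined group.
- That the plan hides what was taken. Dosing, adverse events and deviations are all listed, and QT is also modelled against measured OPC-167832 concentration (protocol 6.3, SAP 11), which does not depend on the arm label.
- That any dosing error is misattributed. A missed or mis-sized dose of the assigned regimen leaves the subject in the right column.

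**Conclusion.** The point holds as a conditional and minor one. The written rule puts every subject in the randomised arm for safety, and no visible text sets a treatment-received rule. A subject who took another arm's regimen would contribute events and QTc values to the wrong arm for a primary endpoint: about 7 percentage points of a 14-subject arm, or 5 points of the pooled RHEZ group.

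This rests on planned arm sizes, on one misclassified subject, and on that subject having taken a different regimen rather than an imperfect version of the assigned one. If that never happens the two groupings give identical tables. No expected size can be computed, because the documents give no error rate. The table shells in SAP Appendices 7 and 8 are not visible, so a footnote or additional display there cannot be ruled out.

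The reason to act in advance is that, without a prespecified rule, any reassignment after an error would be a post hoc choice in an open-label trial.

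**What to change.** In SAP 9, protocol 7.6 and the synopsis, state that the Safety Analysis Set is summarised by treatment actually received, and add:

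- Each subject is classified by the regimen taken on the majority of the days on which that subject was actually dosed within Days 1-14. Ties go to the randomised arm.
- Every subject who took any unassigned study drug is flagged in the safety tables and listed, with the dates taken and the events and QTc values on or after the first such dose.
- Randomised treatment remains the grouping for efficacy and disposition.

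The dosing data needed are already in the eCRF (protocol 3.12). The cost is a wording change in both documents, one derived variable and one listing. The small downside is that arm sizes in safety tables may differ from the randomised counts, which a footnote can explain. No dose or clinical procedure changes.
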